3.2 How will adverse event data be collected/recorded?

Paper AE forms/source documents

3.3. How will AEs be classified/graded?

World Health Organization Criteria (WHO)

NCI Common Toxicity Criteria, Version 2.0/ NCI Common Terminology Criteria, Version 3.0

NCI CTCAE Version 4.0

Mild/Moderate/Severe

Serious/Not serious

3.4 What scale will the PI use when evaluating the relatedness of adverse events to the study participation?

The PI will determine the relationship of adverse events to the study using the following scale:

Related:	AE is clearly related to the intervention
Possibly related:	AE may be related to the intervention
Unrelated:	AE is clearly not related to intervention

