IRB-HSR# 17224: Randomized, Placebo-controlled, Single Blind, Trial to Determine the Safety and Efficacy of Ticagrelor for Maintaining Patency of Arterio-Venous Fistulae Created for Hemodialysis

4. How many subjects will sign a consent form under this UVa protocol?

88

5. Provide an estimated time line for the study.

We hope to have enrollment completed within 6 months of protocol approval.

Inclusion/Exclusion Criteria

1. List the criteria for inclusion

- Patients on chronic hemodialysis with a functioning arterio-venous fistula
- Subjects must agree to use adequate contraception to prevent pregnancy

2. List the criteria for exclusion

- Hemoglobin less than 9g/dL per chart review of the last Hemoglobin level obtained for standard of care.
- If the study subject can't be washed off of anti-coagulants or antiplatelets
- Recent history of bleeding over the last 3 months preceding enrollment
- History of bleeding disorder (hemophilia, Von Willebrandt disease, etc....). Anemia only if it is chronic and thrombocytopenia if the platelet count is consistently <125,000.
- Recent history of blood transfusion over the last 3 months preceding enrollment
- Recent serious injury or surgery over the last 3 months preceding enrollment
- History of gastro-intestinal ulcers
- Moderate-severe hepatic impairment (ALT/AST greater than 3-5 times the upper limit of normal).
- Uncontrolled blood pressure (SBP> 190 or DBP >110) pre or post dialysis
- History of stroke within the last 5 years.
- Pregnant females-self reported
- Hypersensitivity to Aspirin /antiplatelets
- Subjects using peroral anticoagulants
- History of intracranial hemorrhage
- Active pathological bleeding
- Hypersensitivity to ticagrelor or any component of the product

3. List any restrictions on use of other drugs or treatments.

Subjects using peroral anticoagulants will be excluded to avoid excessive bleeding risk. There will be a 4 day wash off for subjects who are taking anticoagulants and anti-platelets. If subjects can't be washed off of these medications then they cannot be included in the study.

Statistical Considerations

1. Is stratification/randomization involved?

Yes

► **IF YES, describe the stratification/ randomization scheme.**

Every other study subject will be on active study drug. Investigators and study personnel will be un-blinded.

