IRB-HSR# 17224: Randomized, Placebo-controlled, Single Blind, Trial to Determine the Safety and Efficacy of Ticagrelor for Maintaining Patency of Arterio-Venous Fistulae Created for Hemodialysis

► IF YES, who will generate the randomization scheme?

UVa Statistician: [name]

2. What are the statistical considerations for the protocol?

Since Ticagrelor has not been used in hemodialysis patients for the purpose of preventing thrombosis in dialysis vascular accesses (Arterio-Venous Fistulae and Grafts), this study is designed as a pilot study in that patients are randomly assigned to receive Ticagrelor or placebo drug for a six-month treatment period plus an additional 6-month follow-up period. The primary objective is to evaluate the feasibility and safety of Ticagrelor in hemodialysis patients with AVF vascular access. The secondary objective is to evaluate the treatment efficacy in that whether Ticagrelor will preserve patency of hemodialysis vascular access better than Placebo. The study will follow intent-to-treat principle and all randomized patients will be included in the analyses for the primary and secondary objectives.

3. Provide a justification for the sample size used in this protocol.

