Due to the pilot nature of this study, formal power analysis and sample size estimation is not essential. Nevertheless, we attempted to estimate the potential treatment efficacy in this study. We considered the outcome measure for efficacy evaluation is the time to first stenosis event during the study period. From our recent clinical data, it was estimated that approximately 36% of dialysis patients experienced stenosis event at one-year follow-up. We would expect that patients in the new drug arm would have 10% stenosis event rate at one-year follow-up, compared to the 36% stenosis event rate in the placebo group. With these considerations, the analysis of stenosis-free survival will require at least 21 events, which is the number of events needed for one-sided log-rank test at 5% significance level to have 80% power to show statistically significant difference when the true hazard ratio is 0.236. This estimation will result in that approximately seventy patients will be needed and evenly randomized into each study arm (35 patients in Ticagrelor and 35 in placebo). This is an open-label study. Upon completion of all the required screening assessments, eligible patients will be randomly assigned to the study drug or placebo at 1:1 ratio with a block size of 20 in accordance with the randomization schedule. The randomization schedule will be provided by the Department of Public Health, School of Medicine. Patients will be identified by unique subject identifier that will remain consistent for the duration of the study. The active study period is 6 months followed by 6 months of monitoring, and accrual rate is approximately 12 patients per month. To compensate for an estimated drop-out rate of 25%, we will recruit 88 patients to the study.

4. What is your plan for primary variable analysis?

We have recruited/consented a total of 54 subjects into this study. We have enrolled a total of 43 patients into the study, 23 in the Ticagrelor treatment arm and 20 in the placebo arm. We will evaluate the safety of Ticagrelor in hemodialysis patients with AVF vascular access by tabulating adverse events and severe adverse events for the two study arms, and the difference between the two arms will be tested by chi-square test.

5. What is your plan for secondary variable analysis?

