2.5 What are the criteria for breaking the blind/mask?

NA – Not blinded/masked

2.6 How will subject withdrawals/dropouts be reported to the IRB prior to study completion?

IRB-HSR continuation status form

3. Adverse Event / Unanticipated Problem Recording and Reporting

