3.1 Will all adverse events, as defined in section 1.1, be collected/recorded?

No

► IF NO, what criteria will be used?

Only adverse events that are deemed related AND serious

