APPENDIX: Pharmacy-Investigational Drugs/Biologics

1. What is the name of the investigational drug/biologic?

Brilinta® (ticagrelor)

2. Where will the subjects be seen for the administration/dispensing of the drug?

 X Outpatient Unit: *specify*: The study drug will be given to dialysis patients at their regularly scheduled dialysis treatment on the 5th floor of the West Complex in the Dialysis Unit

3. What dose will be utilized in this study?

Brilinta® (ticagrelor) - 90mg

4. What will be the frequency of dosing in this study?

Twice a day

5. What will be the duration of dosing in this study?

6 months

6. What route of administration will be utilized?

IRB-HSR# 17224: Randomized, Placebo-controlled, Single Blind, Trial to Determine the Safety and Efficacy of Ticagrelor for Maintaining Patency of Arterio-Venous Fistulae Created for Hemodialysis

Oral

7. Will drug need to be prepared by the UVa Investigational Drug Service (IDS)?

YES

NO- Drug will be prepared and/or administered per package insert

8. Are there any special handling instructions mandated by the study (e.g. weighing hazardous materials)?

No

9. Does the protocol provide provisions for dose titration, dose reductions, and or re-challenged (if drug is stopped), etc.?

No

10. How will missed doses be handled?

If a subject misses a dose we will document the missed dose and the subject will not replace the dose that was missed.

11. Will a comparator (active or placebo) be utilized in the protocol?

Yes

► **IF YES, comparator is:**

Placebo: The placebo medication will be identical in appearance to the active study medication.

12. Does this study involve research on a drug, biologic, supplement or food additive?

Yes

► **IF YES, is this study investigator initiated?**

If yes, answer questions # 13 and 14

If no, answer question # 13 only.

Yes

13. Are you using a drug/supplement/food additive in a manner not approved by the FDA?

Yes

IF YES, answer questions 13a-13f

You may reference the non-IRB protocol to answer these questions.

13a. Describe pertinent animal data that is available regarding the toxicity/safety of this drug.

See section 1 and section 4 of the investigator brochure

13b. Describe pertinent human data that is available regarding the toxicity/safety of this drug.

See section 1 and section 14 of the investigator brochure

13c. Have there been any human deaths associated with this drug?

No

13d. In how many humans has this drug been used previously?

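### If section 3.1 governs, an un-blinded relatedness call decides which serious events are recorded, so the primary safety comparison can be filtered differently by arm

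*Combined protocol and SAP*

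**What the plan says.** Safety belongs to the primary objective: "The primary objective is to evaluate the feasibility and safety of Ticagrelor in hemodialysis patients with AVF vascular access". Statistical Considerations item 4 gives this method for assessing it: "tabulating adverse events and severe adverse events for the two study arms, and the difference between the two arms will be tested by chi-square test". The same item counts 23 subjects on ticagrelor and 20 on placebo.

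Four provisions decide what enters that comparison.

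- Statistical Considerations item 1: "Investigators and study personnel will be un-blinded".
- Data and Safety Monitoring Plan, section 3.4: "The PI will determine the relationship of adverse events to the study using the following scale". The scale has three levels: related, possibly related ("AE may be related to the intervention") and unrelated.
- Section 3.1 answers no to recording all adverse events. The criterion is "Only adverse events that are deemed related AND serious".
- Section 3.7, on reporting of serious adverse events, says that every SAE is documented and that every SAE goes to the drug supplier whatever its causality.

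Section 5.1 names no safety oversight body besides the PI. Section 2.5, on breaking the mask, answers "NA – Not blinded/masked". No masked adjudication of events is described.

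**The concern.** The top level of the scale requires a clear link to the intervention. An assessor who knows that a subject takes placebo has little basis for that call. An assessor who knows that the subject takes ticagrelor can point to bleeding, dyspnea or bradycardia, all listed as drug risks in section 2.1. The same rule can therefore pass different shares of the same events in the two arms. An assessor who expects the drug to be safe could err the other way.

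If the call only described events already on file, this would be a reporting nuance. Section 3.1 makes it a condition for recording. An event judged unrelated then never reaches the table, and no later analysis of the recorded data can restore it. What is at stake is whether the chi-square test measures harm or, in part, the PI's knowledge of treatment.

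**Working it through.** **Tracing the text.** Section 3.1 sets two conditions, seriousness and relatedness. A non-serious event fails in both arms whatever the PI thinks of its cause, so relatedness can decide recording only for serious events. For those events the protocol gives two rules:

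- Section 3.1: record only if also judged related.
- Section 3.7: document all, regardless of cause.

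Two further places lean towards full recording. The 3.7 table lists all adverse events for the FDA annual report, although the Drug Information appendix notes an IND exemption. Section 5.3 lists all adverse events for the PI's aggregate review. Item 4 does not name its source data. Nor do the documents say whether a possibly related event meets 3.1.

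**Illustration.** The plan gives no SAE rate, attribution rate or significance level for the safety test, so there is no figure to reproduce. Inputs:

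- Arm sizes 23 and 20, from item 4.
- True risk of at least one serious event, equal in both arms: 30%, 40% or 50% (assumed).
- Share of subjects with such an event for whom it is called related, by arm (assumed).
- Uncorrected Pearson chi-square, two-sided 5% (assumed).

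Recorded risk = true risk × related-call rate. At 30% true risk and calls of 50% v 10%, recorded risks are 0.30 × 0.50 = 15% and 0.30 × 0.10 = 3%. Expected recorded subjects are 23 × 0.15 = 3.45 and 20 × 0.03 = 0.6. At 40% they are 4.6 v 0.8, and at 50% they are 5.75 v 1.0. The recorded risk ratio is 5 each time, with no true difference.

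The rejection probability is the sum, over every pair of counts (a, b) that the test calls significant, of Bin(a; 23, recorded risk on ticagrelor) × Bin(b; 20, recorded risk on placebo):

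| Related-call rate, ticagrelor v placebo | True risk 30% | 40% | 50% |
|---|---|---|---|
| 50% v 50% | 3.8% | 4.6% | 5.2% |
| 50% v 40% | 4.0% | 5.2% | 6.2% |
| 50% v 30% | 5.7% | 8.5% | 11.1% |
| 25% v 5% | 1.9% | 5.0% | 9.7% |
| 50% v 10% | 15.5% | 28.4% | 40.8% |

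With every SAE recorded, the test rejects in about 5% of trials at each risk. A continuity correction lowers the 28.4% to 16.3%.

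**The other direction.** Take true risks of 60% on ticagrelor and 30% on placebo. With every SAE recorded, power is 53%. If 30% of ticagrelor and 50% of placebo events are called related, recorded risks are 0.60 × 0.30 = 18% and 0.30 × 0.50 = 15%, and the chance of a significant result in the harm direction falls to 3%.

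**The case against.** The strongest reply is that the filter is contradicted exactly where it would act. Relatedness matters only for serious events, and section 3.7 requires all of those to be documented. If 3.7 governs and its SAEs feed item 4, relatedness removes nothing from the SAE comparison. This stands, and it makes the concern conditional. It does not dispose of it, because 3.1 is the protocol's explicit recording rule and item 4 does not say which set it uses.

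A reader might infer that harms are in fact ascertained differently by arm. The documents do not show this: a PI could call events related at the same rate in both arms, and the first row of the table then shows no inflation, only lost information.

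A reader might also infer that the comparison stays biased even with every SAE documented, through a by-arm table of related events. Item 4 plans no such table and sets no relatedness condition.

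Nor should 16% to 41% be read as the trial's error rate. Nothing in the documents supports 50% v 10%. If possibly related events pass the filter, the gap between arms could be narrow, and 50% v 40% leaves the test close to nominal.

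Finally, a masked grader may seem the natural remedy, since "The placebo medication will be identical in appearance to the active study medication". But current personnel already know the arms, so an additional assessor would be needed. Masked grading would also still discard events while 3.1 stood.

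In the concern's favour, the relatedness call also bears on IRB reporting (3.7) and on stopping treatment (2.3). A change to recording does not alter those uses.

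**Conclusion.** The concern holds in conditional form. If section 3.1 governs, an un-blinded judgement decides which serious events are recorded, and the primary chi-square comparison can then be distorted in either direction. Sections 3.1 and 3.7 conflict, and item 4 does not settle which event set is analysed.

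The size and direction of any bias cannot be found from the documents. Across the assumed scenarios with equal true risk and unequal calls, false rejection at 23 v 20 runs from 2% to 41%. The upper end needs both a wide gap in attribution and a high event rate. These figures rest on assumed risks and call rates, one serious-event indicator per subject, and an uncorrected two-sided 5% test. Item 4 speaks of severe events where 1.2 and 3.1 speak of serious ones; the working treats them as serious.

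**What to change.** - Amend section 3.1 to agree with 3.7 and 5.3: adverse events and all SAEs are recorded in both arms regardless of relatedness.
- State in Statistical Considerations item 4 that the by-arm tabulation and the chi-square test use that full set and do not condition on relatedness.
- Report relatedness descriptively only, labelled as judged un-blinded.
- For the 43 subjects already enrolled, recover unrecorded SAEs from source documents and from the SAE reports sent to the drug supplier.

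Both amendments are needed. Telling item 4 to ignore relatedness achieves nothing if 3.1 has already removed the unrelated events.

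The cost is more adverse event forms and some retrospective record review, with no extra subjects or visits. A grader masked to arm would make the descriptive relatedness table more credible, but that is optional and not part of the required change.

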3.5 When will recording/reporting of adverse events/unanticipated problems begin?

After subject begins study drug/ device placement/intervention /study-related procedure/specimen collection

3.6 When will the recording/reporting of adverse events/unanticipated problems end?

IRB-HSR# 17224: Randomized, Placebo-controlled, Single Blind, Trial to Determine the Safety and Efficacy of Ticagrelor for Maintaining Patency of Arterio-Venous Fistulae Created for Hemodialysis

_____ End of study drug/device/intervention/participation

_____ 30 days post study drug/device/intervention

X Subject completes intervention and follow up period of protocol

3.7 How will Adverse Events, Unanticipated Problems, Protocol Violations and Data Breaches be reported? Complete the table below to answer this question

Type of Event	To whom will it be reported:	Time Frame for Reporting	How reported?
Any internal event resulting in death that is deemed DEFINITELY related to (caused by) study participation An internal event is one that occurs in a subject enrolled in a UVa protocol	IRB-HSR	Within 24 hours	IRB Online and phone call www.irb.virginia.edu/
Internal, Serious, related and Unexpected adverse event	IRB-HSR	Within 7 calendar days from the time the study team received knowledge of the event. Timeline includes submission of signed hardcopy of AE form.	IRB Online www.irb.virginia.edu/
Unanticipated Problems that are not adverse events or protocol violations This would include a Data Breach.	IRB-HSR	Within 7 calendar days from the time the study team received knowledge of the event.	Unanticipated Problem report form. http://www.virginia.edu/vprgs/irb/HSR_docs/Forms/Reporting_Requirements-Unanticipated_Problems.doc
Protocol Violations (The IRB-HSR only requires that MAJOR violation be reported, unless otherwise required by your sponsor, if applicable.) Or Enrollment Exceptions See definition- only allowed if there is a commercial sponsor or a DSMB that has granted the enrollment exception.	IRB-HSR	Within 7 calendar days from the time the study team received knowledge of the event.	Protocol Violation and Enrollment Exception Reporting Form http://www.virginia.edu/vprgs/irb/hsr_forms.html Go to 3rd bullet from the bottom.

IRB-HSR# 17224: Randomized, Placebo-controlled, Single Blind, Trial to Determine the Safety and Efficacy of Ticagrelor for Maintaining Patency of Arterio-Venous Fistulae Created for Hemodialysis

Data Breach	The UVa Corporate Compliance and Privacy Office, a	As soon as possible and no later than 24 hours from the time the incident is identified.	UVa Corporate Compliance and Privacy Office- [contact]
	ITC: if breach involves electronic data-	As soon as possible and no later than 24 hours from the time the incident is identified. IMMEDIATELY.	ITC: Information Security Incident Reporting procedure, http://www.itc.virginia.edu/security/reporting.html
	UVa Police if breach includes such things as stolen computers.		Phone- [contact]

UVa PI HELD IND			
Type of Event	To whom will it be reported:	Time Frame for Reporting	How reported?
Life-threatening and/or fatal unexpected events related or possibly related to the use of the investigational agent.	FDA	Within 7 calendar days of the study team learning of the event	Form FDA 3500A (MedWatch) or narrative
Serious, unexpected and related or possibly related adverse events	FDA	Within 15 calendar days after the study team receives knowledge of the event	Form FDA 3500A (MedWatch) or narrative
All adverse events	FDA	Annually	IND annual report

Reporting of serious adverse events

Investigators and other site personnel must inform the FDA, via a MedWatch/AdEERs form, of any serious or unexpected adverse events that occur in accordance with the reporting obligations of 21 CFR 312.32, and will concurrently forward all such reports to AZ. A copy of the MedWatch/AdEERs report must be faxed to AstraZeneca at the time the event is reported to the FDA. It is the responsibility of the investigator to compile all necessary information and ensure that the FDA receives a report according to the FDA reporting requirement timelines and to ensure that these reports are also submitted to AstraZeneca at the same time.

When reporting to AstraZeneca, a cover page should accompany the MedWatch/AdEERs form indicating the following:

- Investigator Sponsored Study (ISS)
- The investigator IND number assigned by the FDA
- The investigator’s name and address
- The trial name/title and AstraZeneca ISS reference number

Investigative site must also indicate, either in the SAE report or the cover page, the causality of events in relation to all study medications and if the SAE is related to disease progression, as determined by the principal

IRB-HSR# 17224: Randomized, Placebo-controlled, Single Blind, Trial to Determine the Safety and Efficacy of Ticagrelor for Maintaining Patency of Arterio-Venous Fistulae Created for Hemodialysis

investigator. Send SAE report and accompanying cover page by way of fax to AstraZeneca’s designated fax line: [name]. Serious adverse events that do not require expedited reporting to the FDA need to be reported to AstraZeneca preferably using the MedDRA coding language for serious adverse events. In the case of blinded trials, AstraZeneca will request that the Sponsor either provide a copy of the randomization code/ code break information or unblind those SAEs which require expedited reporting. All SAEs have to be reported to AstraZeneca, whether or not considered causally related to the investigational product. All SAEs will be documented. The investigator is responsible for informing the IRB and/or the Regulatory Authority of the SAE as per local requirements.

Serious adverse events that do not require expedited reporting to the FDA need to be reported to AstraZeneca on a quarterly basis preferably using the MedDRA coding language for serious adverse events.

4. How will the endpoint data be collected/recorded.

- Protocol specific case report forms
- Source documents

5. Data and Safety Oversight Responsibility

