2.1 What are identified risks and plans to minimize risk

****Please Also Refer to the Investigator Brochure and the Package Insert for Brilinta/ Ticagrelor**

Adverse Events with Brilinta/Ticagrelor

Frequent complaints (seen in at least 3% of study participants) that have been reported during studies:

- Bleeding
- Dyspnea (Shortness of Breath)
- Cough
- Dizziness
- Nausea
- Atrial Fibrillation (Heart Rhythm Disorder)
- Hypertension (High Blood Pressure)
- Non-Cardiac Chest Pain

IRB-HSR# 17224: Randomized, Placebo-controlled, Single Blind, Trial to Determine the Safety and Efficacy of Ticagrelor for Maintaining Patency of Arterio-Venous Fistulae Created for Hemodialysis

- Diarrhea
- Back Pain
- Hypotension (Low Blood Pressure)
- Fatigue
- Chest Pain
- Headache

More Frequent complaints (seen in at least 6 to 7% of study participants) that have been reported during studies:

- Bradycardia (Slow Heart Rate)
- Elevated Serum Creatinine

There have also been cases of increased uric acid levels for subjects taking ticagrelor. A high uric acid level, or hyperuricemia, is an excess of uric acid in your blood. Uric acid is produced during the breakdown of purine, a substance found in many foods. Once produced, uric acid is carried in your blood and passes through your kidneys, where most of it leaves your body when you urinate. A high uric acid level may result in attacks of gout, but not everyone who has high uric acid gets gout, and not everyone with gout has high uric acid. Increased uric acid may also increase the chances of kidney stones. There is also an increased risk of severe bleeding for subjects taking ticagrelor. Due to the increase risk of severe bleeding there may be a risk of delay in any surgery that you may need while taking this study medication.

Expected Risks related to study participation.	Frequency
Reproductive Risks These are unknown at this time.	Minimized due to the requirements of this protocol.
Violation of subject’s privacy and confidentiality	Minimized due to the requirements of the privacy plan in this protocol

2.2 List by bullet format a summary of safety tests/procedures/observations to be performed that will minimize risks to participants:

- Study personnel will be checking on patients twice a month for six months while subjects are on study treatment and once a month while subjects are in the follow up visits.
- We will be monitoring the time it takes for the subject’s access to clot.
- AE monitoring at each visit

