5.1. Who is responsible for overseeing safety data for this study ?

- No additional oversight body other than PI at UVa Skip question 5.2

5.2. What is the composition of the reviewing body and how is it affiliated with the sponsor? N/A

5.3. What items will be included in the aggregate review conducted by the PI?

- All adverse events
- Unanticipated Problems
- Protocol violations
- Audit results
- Application of dose finding escalation/de-escalation rules

These should be outlined under 2.4.
- Application of study designed stopping/decision rules
- Early withdrawals
- Whether the study accrual pattern warrants continuation/action
- Endpoint data

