APPENDIX: Drug Information

1. What is the drug name, manufacturer and IND# if available?

Drug Name: Ticagrelor (Brilinta) and Placebo, Manufacturer: Astra Zeneca
IND exempt notification from FDA on file

2. If IND application has been submitted to the FDA, who is the Principal Investigator on the IND?

[name]

3. What is the phase or stage of this study?

Pilot

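### The expedited-reporting rules in section 3.7 do not match the plan's own relatedness scale and contradict each other: read literally, a serious event graded possibly related meets no dated IRB row

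*Combined protocol and SAP*

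**What the plan says.** **IRB rows (section 3.7).** Three rows of the table bear on this. The 24-hour row covers "Any internal event resulting in death that is deemed DEFINITELY related to (caused by) study participation". The first 7-day row covers "Internal, Serious, related and Unexpected adverse event". A further 7-day row covers "Unanticipated Problems that are not adverse events or protocol violations".

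**Relatedness (3.4).** The investigator grades each event as related (clearly so), possibly related (may be so) or unrelated (clearly not).

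**Expectedness.** Section 1.3 explains *unexpected* only for unanticipated problems, by nature, severity or frequency, judged against the protocol-related documents and the study population. Its relatedness criterion accepts a possible relation. Section 2.1 lists bleeding among the frequent complaints and adds: "There is also an increased risk of severe bleeding for subjects taking ticagrelor". It also refers the reader to the investigator brochure and the package insert.

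**FDA rules (3.7, table headed as a PI-held IND).** The 7-day row takes fatal or life-threatening events that are unexpected and at least possibly related. The 15-day row takes "Serious, unexpected and related or possibly related adverse events". The narrative below the table tells sites to inform the FDA "of any serious or unexpected adverse events that occur in accordance with the reporting obligations" of a cited regulation. The Drug Information appendix, item 1, states "IND exempt notification from FDA on file".

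**Other routes and oversight.** The narrative sends all serious adverse events to the drug supplier whatever their causality, quarterly if they are not expedited. It also makes the investigator responsible for informing the IRB and/or the authority according to local requirements, with no time limit. Section 5.1 records "No additional oversight body other than PI at UVa", and section 5.4 sets the aggregate review at once a year.

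**The concern.** Evaluating safety is part of the trial's primary objective. The Background says the drug was never tested in patients with ESRD, and severe bleeding is a harm that the plan itself names. Section 2.4 lets the IRB stop the study, and no data monitoring board is constituted, so the IRB is the body outside the study team that most needs timely notice of serious events.

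The IRB rows use relatedness terms that the grading scale does not supply, or supplies only in part. A coordinator holding a serious bleed graded *possibly related* finds no dated IRB row that clearly fits. The coordinator then finds two FDA rules that can give different answers, under a heading that may not apply to this study. Section 3.1 adds to the difficulty by limiting recording to events that are both related and serious, while the narrative in 3.7 requires every serious adverse event to be documented. The route taken may then depend on who reads the form.

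**Working it through.** No sample size, power or event rate enters here, so the check is a decision table. Take a serious bleed graded *possibly related*. Cross its outcome (fatal, life-threatening, other serious) with its class (expected, unexpected): 3 × 2 = 6 cases. Then apply each written trigger.

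Triggers used:
- IRB 24-hour row: death and definitely related. Expectedness plays no part.
- IRB 7-day row: serious and related and unexpected.
- IRB unanticipated-problem row: excludes adverse events, so it catches no bleed.
- FDA table: unexpected and at least possibly related, at 7 days if fatal or life-threatening and 15 days if otherwise serious.
- FDA narrative, read literally: serious or unexpected.

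| Case | IRB, literal | IRB, possible counted as related | FDA table | FDA narrative |
|---|---|---|---|---|
| Fatal, unexpected | no | 7 days | 7 days | yes |
| Fatal, expected | no | no | no | yes |
| Life-threatening, unexpected | no | 7 days | 7 days | yes |
| Life-threatening, expected | no | no | no | yes |
| Other serious, unexpected | no | 7 days | 15 days | yes |
| Other serious, expected | no | no | no | yes |
| **Triggered** | **0 of 6** | **3 of 6** | **3 of 6** | **6 of 6** |

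Three things follow.

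1. **Relatedness.** The whole difference between 0 and 3 of 6 in the IRB columns comes from whether *related* in the 7-day row includes *possibly related*. The FDA rows and section 1.3 both spell out the possible level, and this row does not. *Definitely*, in the 24-hour row, is not a level of the 3.4 scale at all.

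2. **Expectedness.** In the three expected cases the dated IRB rows give 0 of 3 on either reading, and the FDA table gives 0 of 3. The column a bleed falls in therefore decides its route, and no section says how to place it. Non-fatal serious bleeding can be placed in the expected column on the strength of 2.1.

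3. **FDA rules.** For an expected serious bleed the table gives 0 of 3 and the narrative 3 of 3. Both FDA columns assume that the FDA route operates. The table heading and the supplier cover page, which asks for an IND number, suggest that it does. The Drug Information appendix reports an exemption.

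Adding the possible level to the 7-day IRB row moves the literal count from 0 to 3 of 6. The remaining three cases depend on how expectedness is defined.

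**The case against.** The strongest reply is that these rows answer an institutional form and state what that IRB asks for, so a wider trigger is a preference. Section 1.3 of the same form accepts a possible relation, which suggests that the shorter wording in the 7-day row is drafting and not a deliberate exclusion. That is plausible, but it supports writing the words in, because the literal text says otherwise.

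A reader might infer that a fatal bleed would escape expedited review. The documents do not establish this. Only bleeding and severe bleeding are listed. Section 1.3 counts severity as a ground for calling an event unexpected. Item 13c of the pharmacy appendix answers no to human deaths associated with the drug. On these texts a fatal bleed can readily be classed as unexpected, and the FDA 7-day row, if it applies, would then take it when possibly related. A death judged definitely related goes to the IRB in 24 hours even if expected. The investigator brochure and package insert, which might settle the matter, are not part of the documents.

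A reader might also infer that the safety signal would stay with the investigator. That goes too far: the supplier receives all serious adverse events, and the sentence on local requirements may bring them to the IRB. Still, the supplier is stated not to be monitoring the study, and that sentence carries no deadline.

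Finally, the FDA narrative is qualified by a regulation, which may have been meant to align it with the table. The text itself does not do so.

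**Conclusion.** The point holds as a defect of wording and consistency in the reporting rules. On a literal reading, 0 of 6 cases of a serious bleed graded *possibly related* meet a dated IRB row, and 3 of 6 do so if possible is counted as related. An expected non-fatal serious bleed can miss both the IRB rows and the FDA table, while the FDA narrative would include it. The conflicts between the FDA table and its narrative, and between the PI-held IND heading and the IND exemption, stand on the text alone.

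The size cannot be put as a number of events. The documents give no rate of serious bleeding, so any count would rest on an assumed risk. Nor do the documents show that every death whatever its relatedness, or every expected serious bleed, must be expedited; that would be a preference beyond the inconsistency shown.

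The conclusion assumes that the 3.4 levels are the ones applied in 3.7, and that the unseen local requirements do not already set a dated route for these events. It should be corrected, because the investigator is the only safety overseer and the aggregate review is annual.

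**What to change.** Make four changes in one amendment:

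1. Add the possible level to the 7-day IRB row, and express the 24-hour row in the levels of the 3.4 scale.
2. Name the document against which *unexpected* is judged for adverse event reporting, and state how serious bleeds, fatal and non-fatal, are classed in this ESRD population.
3. Reconcile the FDA table with the narrative below it, and state whether the FDA rows apply given the IND exemption.
4. Reconcile the recording limit in 3.1 (related and serious only) with the statement in 3.7 that every serious adverse event is documented, so that possibly related serious events are recorded.

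The changes concern reporting and recording only and leave clinical management as it is. The cost is the amendment itself and a few extra IRB reports.
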